## 2. STUDY PURPOSE AND GOALS

### STUDY GOAL

It is intended that the results of this Human Factors Validation Testing be used to support an over-the-counter (OTC) use indication for the LunulaLaser™ OTC for the temporary increase of clear nail in patients with onychomycosis (e.g., dermatophytes *Trichophyton rubrum* and *T. mentagrophytes*, and/or yeasts *Candida albicans*, etc.). The indication for use is identical to the predicate device, the LunulaLaser™ cleared under K153164, with the only difference being the designation of Over-the-Counter (OTC) use. The LunulaLaser™ OTC delivers a nonthermal and non-invasive procedure designed to restore growth of clear, healthy nails in clients with onychomycosis without harmful side effects of oral medication, or the pain and recovery time associated with other laser treatments. Therefore, it is intended that the results of this Human Factors Validation Testing will demonstrate that the LunulaLaser™ OTC can be used by the intended users without serious errors or problems for the intended use and under the expected use conditions.

### 2.1. PURPOSE OF STUDY

The purpose of the LunulaLaser™ OTC Human Factors Validation Testing is to:

- (i) evaluate the intended user's ability to correctly, safely and effectively set-up, activate and operate the LunulaLaser™ OTC to administer the treatment to the client;
- (ii) evaluate the intended user's ability to understand and apply as applicable the information contained in the LunulaLaser™ OTC Use Device Installation and Proper Use Reference Guide, and device packaging and labeling materials; and
- (iii) identify any and all use difficulties, problems and errors, including those pertaining to critical tasks and close calls demonstrated by intended users during device operation, and to subsequently mitigate each identified instance of use error through device and/or materials modification, and to subsequently evaluate the effectiveness of each modification, as applicable.

### 3. STUDY DEVICE: LUNULALASER™ OTC; ERCHONIA® CORPORATION

The LunulaLaser™ OTC (Figure 1) is intended to be indicated for the temporary increase of clear nail in patients with onychomycosis (e.g., dermatophytes *Trichophyton rubrum* and *T. mentagrophytes*, and/or yeasts *Candida albicans*, etc.)

The LunulaLaser™ OTC is a nonthermal and non-invasive procedure designed to restore growth of clear, healthy nails in clients with onychomycosis without harmful side effects of oral medication, or the pain and recovery time associated with other laser treatments.

Figure 1: LunulaLaser™ OTC

The LunulaLaser™ OTC works by using a patented and clinically proven low-level laser technology. The Lunula laser combines two different wavelength lasers; one visible violet light (about 405 nanometer wavelength) for direct fungicidal activity and one visible red light (about 635 nanometer wavelength) to stimulate a natural immune response. The two lasers work together to increase clear nail in individuals with toenail onychomycosis.

The LunulaLaser™ OTC device and the intended use to be evaluated in this Human Factors Validation Study is identical to that which was cleared by FDA on June 3, 2016 for prescription use, as follows:

#### 510(k) # K153164

Product Code: PDZ

Class II

Device Name: LunulaLaser

Indications for Use: The LunulaLaser™ device is indicated for use for the temporary increase of clear nail in patients with onychomycosis (e.g., dermatophytes *Trichophyton rubrum* and *T. mentagrophytes*, and/or yeasts *Candida albicans*, etc.)

Additional device details are contained in the **Installation and Proper Use Reference Guide** contained in **Appendix B**.

## 4. STUDY DESIGN

This study is an uncontrolled simulated-use human factors validation testing design to assess the intended user's ability to correctly, safely, and effectively set-up, activate and operate the LunulaLaser™ OTC, to administer a treatment to a client, and to understand the information contained in the Erchonia LunulaLaser™ OTC Installation and Proper Use Reference Guide and box labeling.

The study design is comprehensive in scope and conducted in a manner such that the results will be able to be generalized to the actual intended user and under intended conditions of actual use and be adequately sensitive to capture use errors arising from either the user interface design and/or the instructional and informative materials. Study data will be collected in a manner that will facilitate analysis of the root causes of use errors or problems during the testing.

### 4.1. STUDY DESIGN ELEMENTS

The key elements of the study design that support its ability to generalize study results to the intended user under intended use conditions are the following:

- (i) Users (test participants) will represent the intended (actual) users of the LunulaLaser™ OTC; that is, users will be employees at nail salons, beauty salons and spas, fitness and wellness centers, and the like;
- (ii) All critical tasks will be performed, observed and evaluated during the testing;
- (iii) The device user interface and all associated instructional/informational materials will represent the final intended post-clearance (actual use) design; and
- (iv) The simulated-use test conditions will be sufficiently realistic to represent the actual intended conditions of use. Under actual intended conditions of use, the user will receive the Erchonia LunulaLaser™ OTC device in its full packaging via delivery to the facility at which they are employed and will need to rely on the information/instructional information contained in the Installation and Proper Use Reference Guide and the device and packaging labeling to configure and operate the device for use.

(v) In this study, the user will simply be presented with the device in its intended packaging as if receiving it at their place of employment. No additional information, instruction or training will be provided by the Study Observer, or any other individual associated with the study. The user will be left to work out how to operate the Erchonia LunulaLaser™ OTC as independently and naturally as possible without interference or influence from the Study Observer. While the user will have received the instructional information in the packaging as in intended use, he or she will not be instructed to use any of the information. It will be up to the user as to if or how he or she chooses to use that information to set up operation of the device as would occur under actual conditions of intended use.

## **5. CRITICAL TASKS ANALYSIS**

**5.1. CRITICAL TASK:** For the purpose of the critical tasks analysis for this study, a critical task is defined as a user task which, if performed incorrectly (use error) or not performed at all, would or could cause serious harm to the patient or user, where harm is defined to include compromised medical care (use-related hazard). Critical task analysis is part of the device risk analysis.

**5.2. USER TASK:** A user task is defined as an action or set of actions performed by a user to achieve a specific goal i.e., safe, and effective use of the device for the intended purpose.

**5.3. USE ERROR:** Use error is defined as a user action or lack of action that is different from that expected by the manufacturer and caused a result that was different from the result expected by the user; was not caused solely by device failure; and did or could result in harm.

## **5.4. HAZARDS**

**5.4.1. Non-Use Related Hazards:** A non-use related hazard is a potential source of harm that is generally associated with instances of device or component failure that are not dependent on how the user interacts with the device.

Non-use related hazards traditionally considered in risk analysis include:

- Physical hazards (e.g., sharp corners or edges),
- Mechanical hazards (e.g., kinetic or potential energy from a moving object),
- Thermal hazards (e.g., high-temperature components),

- Electrical hazards (e.g., electrical current, electromagnetic interference (EMI)),
- Chemical hazards (e.g., toxic chemicals),
- Radiation hazards (e.g., ionizing and non-ionizing), and
- Biological hazards (e.g., allergens, bio-incompatible agents and infectious agents).

**5.4.2. Use-Related Hazards:** A use-related hazard is a potential source of harm derived from incorrect performance or lack of performance of a critical task by the device user interactions with the device. These hazards might result from aspects of the user interface design that cause the user to fail to adequately or correctly perceive, read, interpret, understand, or act on information from the device.

Use-related hazards are related to one or more of the following situations:

- Device use requires physical, perceptual, or cognitive abilities that exceed the abilities of the user;
- Device use is inconsistent with the user's expectations or intuition about device operation;
- The use environment affects operation of the device and this effect is not recognized or understood by the user;
- The particular use environment impairs the user's physical, perceptual, or cognitive capabilities when using the device;
- Devices are used in ways that the manufacturer could have anticipated but did not consider; or
- Devices are used in ways that were anticipated but inappropriate (e.g., inappropriate user habits) and for which risk elimination or reduction could have been applied but was not.

Both non-use related and use-related hazards associated with the Erchonia LunulaLaser™ OTC have been included in the risk analysis and management process.

**5.5 ANALYTICAL APPROACHES:** Analytical approaches for identifying non-use related and use-related hazards (critical task analysis) include analysis of the expected needs of users of the new device, analysis of available information about the use of similar devices, and employment of one or more analytical methods.

**5.5.1. Task Analysis Technique:** Critical tasks analysis was conducted using the task analysis technique, defined as the process of studying how users of the device would likely perform each task and the potential use errors that may occur if any of the identified tasks are performed incorrectly or not performed at all. User interactions with the design interface will be examined with respect to perceptual inputs, cognitive processing and physical actions that comprise the successful execution of each individual task. Potential user errors that may arise from each of these task components will be analyzed to identify the potential consequences of the errors and the potential resulting harm from the errors. This comprehensive identification and categorization of user tasks led to the identification and development of the list of critical tasks that users should perform correctly for use of the Erchonia LunulaLaser™ OTC to be safe and effective.

For this identified list of critical tasks, each individual critical task was categorized based on the severity of the potential harm that could result from use error(s), as identified in the risk analysis, with the goal of identifying the task(s) that, if performed incorrectly or not performed at all, would or could cause serious harm.

**5.5.2. Failure Modes Effects Analysis (FMEA):** The risk analysis approach employed a team-based failure modes effects analysis (FMEA) to identify potential use errors and the potential harm that could result from each potential use error related to the user-device interaction as comprehensively as possible.

All risks associated with the warnings, cautions and contraindications in the labeling are included in the risk assessment.

The final list of critical tasks was used to structure the human factors validation test to ensure it focuses on the tasks that relate to device use safety and effectiveness. While every effort has been made to identify and consider all critical tasks, associated use errors and potential resultant harm to the user and/or patient from use error, it is possible that some potential use errors might not be recognized until the human factors validation testing is conducted. The test protocol therefore includes mechanisms to detect previously unanticipated use errors.

As part of the risk analysis process, **identification of known use-related problems**, if any, that have occurred with the use of similar devices with regards to use, the user interface or user

interactions, will be identified, considered, and evaluated as applicable to the Erchonia LunulaLaser™ OTC.

## 5.6. OUTCOME OF THE CRITICAL TASK ANALYSIS

Through the task analysis approach, the critical device analysis was conducted by systematically breaking down the device use process into discrete sequences of tasks. Each identified task was then analyzed to identify the user interface components involved, the potential use errors (with respect to each of potential perceptual, cognitive processing and physical errors, as applicable) that users could make and the potential results (consequences and harm) of each of those use errors, as well as the mitigation (method of control) in place to prevent or minimize the use error from occurring and/or to reduce the severity of potential harm in the event that the use error is still made.

Each potential use error was further categorized according to the probability or likelihood of the use error the associated hazard occurring, the severity of the potential associated hazard(s) were it to occur, and the risk level (Probability/Likelihood X Severity), according to the Tables 1, 2 and 3, respectively, below.

**Table 1: PROBABILITY OF OCCURRENCE**

Category	Rating	Description
Frequent	5	Likely to occur about once every 100 uses.
Probable	4	A use error/hazard likely to occur about every 10,000 uses or about every 2 years of expected use.
Occasional	3	A hazard likely to cause harm every 100,000 uses or only on one of two systems over their 10 year expected lives.
Remote	2	A hazard likely to cause harm every 1,000,000 uses or only on one of twenty-one systems over their expected lives.
Improbable	1	A use error hazard likely to cause harm every 10 million uses or on no currently installed systems within their 10 year expected lives (assumes current installed base does not exceed 210 systems within 10-year period).

**Table 2: SEVERITY**

Rating	Rating	Description
Catastrophic	5	Results in death
Critical	4	Results in permanent impairment or life-threatening injury

Serious	3	Results in injury or impairment requiring medical intervention
Minor	2	Results in injury or impairment not requiring medical intervention
Negligible	1	Inconvenience or temporary discomfort

Probability Rating	Severity Rating				
	1	2	3	4	5
5	5	10	15	20	25
4	4	8	12	16	20
3	3	6	9	12	15
2	2	4	6	8	10
1	1	2	3	4	5

The outcome of the critical tasks analysis is contained in **Appendix A**.

## 6. STUDY PARTICIPANT AND ENVIRONMENTAL DESIGN

### 6.1. SUBJECTS (USERS and CLIENTS)

#### 6.1.1. USER SAMPLE

The study user sample will be representative of the population of intended users of the device who are employees at nail salons, beauty salons and spas, fitness and wellness centers, and the like.

In defining the device user and the potential impact of the device user characteristics on the user's ability to safely, and effectively, use the device, the following personal characteristics were considered and evaluated, with the outcome as follows:

Device User Characteristic	Outcome of Consideration
Physical size, strength, and stamina	Able to lift and carry 23lbs / 10.43 kg
Physical dexterity, flexibility, and coordination	Able to plug the power cord into the device and an electrical outlet; operate the key to turn the device on and off; open and close the magnetic door/foot platform using the knobs; operate the touchscreen; and correctly place the safety glasses on themselves and the client.

Sensory abilities such as vision, hearing, and tactile sensitivity	Able to read the information on the device screen display.
Cognitive abilities, including memory	Able to understand the instructions in the Installation and Proper Use Reference Guide for safe and effective use of the device; able to understand when to use the device and how to confirm client eligibility.
Medical condition for which the device is being used	n/a
Comorbidities	n/a
Literacy and language skills	English language; 5 th Grade literacy skills.
General health status	n/a
Mental and emotional state	Sufficient stability.
Relevant level of education and health literacy	Able to read at 5 th Grade level; aware of client eligibility criteria.
General knowledge of similar types of devices	Not necessary but beneficial.
Knowledge of and experience with the particular device	n/a
Ability to learn and adapt to a new device	Sufficient ability.
Willingness and motivation to learn to use a new device	Sufficient willingness and motivation.

In considering these specific characteristics of intended device users that may affect their interactions with the device, given the typical profile of the intended users of the LunulaLaser™ OTC, it was determined that there did not need to be specific evaluation of potential users within any of these specific device user categories.

Additionally, the development and design of the Erchonia LunulaLaser™ OTC and the Installation and Proper Use Reference Guide was modelled on the existing Installation and Proper Use Reference Guide for Erchonia Corporation's currently market cleared OTC device, the Erchonia Zerona Z6 OTC (K162578; K143007) indicated for: "The Zerona® Z6 OTC device is indicated for use as a non-invasive dermatological aesthetic treatment for the reduction of circumference of

hips, waist, and thighs.” The user sample in the Human Factors Validation Study whose results supported the market clearance for the Zerona Z6 OTC is comparable to that being evaluated in the current Human Factors Validation Study; that is, users in the prior study were employees of Fitness and Wellness centers and like facilities.

As in this current study, the only training device users received in the human factors evaluation of the Zerona Z6 OTC was that contained in the Installation and Proper Use Reference Guide and device packaging and labeling.

#### **6.1.1.1. User Sample Eligibility Criteria**

To qualify for study participation, the user must satisfy each of the following inclusion criteria and none of the exclusion criteria.

##### Inclusion Criteria

1. 18 years or older.
2. Male or female.
3. Currently employed at a nail salon, beauty salon and/or spa, fitness and wellness centers, or the like.
4. In possession of qualification(s), current licensure(s), certification(s), and/or accreditation(s), as applicable, to perform their designated tasks at their place of employment, e.g., cosmetology degree, nail technician, esthetician, massage therapist, etc.
5. Voluntarily signed consent form.

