#### **6.1.1.2. User Sample Size**

As per the United States Food and Drug Administration (U.S. FDA) document titled ‘Applying Human Factors and Usability Engineering to Medical Devices: Guidance for Industry and Food and Drug Administration Staff’; February 3, 2016, Section 8.1.1 Test Participants (Users), the minimum number of 15 subjects is required to be enrolled in and complete this study. The minimum sample size of 15 subjects is applicable as the intended actual user population in this validation study is a homogenous group of adults who are applicably qualified/licensed/certified/

accredited employees at cosmetology-related facilities such as nail salons, beauty salons and/or spas, fitness and wellness centers, or the like.

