#### **6.1.1.3. User Sample Recruitment**

The subject user sample will be recruited from nail salons, beauty salons and/or spas, fitness and wellness centers, or the like, in the geographical area within the vicinity of the test location.

A potential candidate who voluntarily signs the informed consent form and subsequently satisfies the enrollment criteria will be enrolled as a User in this Human Factors Validation Testing study.

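### Eligibility lets in people already trained on the identical prescription device and sets no spread across facility types, so a test of untrained use could miss use errors

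*Combined protocol and SAP*

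**What the plan says.** Section 4 sets the aim: results should carry over to the actual intended users under actual conditions of use, and the test should be sensitive enough to capture use errors. Section 2.1 (iii) makes finding use difficulties, errors and close calls a purpose of the study. Section 4.1 (v) states that "No additional information, instruction or training will be provided by the Study Observer, or any other individual associated with the study". Sections 7.2.3 and 7.2.4 repeat that there is no training and ask the user to act as though the device had newly arrived at work.

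Section 6.1.1.1 has five inclusion criteria: age, sex, employment, applicable qualification and consent. The employment criterion is "Currently employed at a nail salon, beauty salon and/or spa, fitness and wellness centers, or the like". The exclusion list is empty. Section 3 says that the device and its intended use are identical to those cleared for prescription use in June 2016. The protocol is dated May 2021.

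The user-characteristics table in 6.1.1 enters n/a for experience with this particular device and rates general knowledge of similar devices "Not necessary but beneficial". It also gives English and 5th "Grade literacy skills" as the expected reading level. It concludes that potential users need no specific evaluation on these characteristics. The same section says that the Guide was modelled on that of the sponsor's marketed Zerona Z6 OTC, and that "users in the prior study were employees of Fitness and Wellness centers and like facilities".

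Section 6.1.1.2 states that "the minimum number of 15 subjects is required to be enrolled in and complete this study" and justifies this by saying that "the intended actual user population in this validation study is a homogenous group of adults". Section 6.1.1.3 recruits "in the geographical area within the vicinity of the test location", with no number per facility type. Section 6.2 lists three named settings plus comparable facilities.

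**The concern.** Withholding training in the test room secures untrained use only if the user was not trained elsewhere. The prescription version had been on the market route for almost five years when this protocol was written, and nothing in 6.1.1.1 keeps its users or trainees out. Such a person brings knowledge that the box and Guide did not supply. Any error that this knowledge prevents is one the test was meant to reveal, and a use error that is never seen gets no root-cause analysis, mitigation or retest under 11.2.

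The second gap is spread. A sample drawn entirely from, say, nail salons near the test site would comply fully with the protocol. It would then be offered as evidence for spas and fitness centers as well, and the only support for that step is the statement that the users are homogenous.

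**Working it through.** **The plan's own figure.** The 15 is a minimum taken from the cited guidance together with the homogeneity statement. Section 6.1.1.2 gives no error rate, power or margin, so no formula can reproduce it, and it is not disputed here. The question is what 15 users can show if they are not all naive or not all from different settings.

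**1. Error detection when some users are experienced.** Let p be the share of naive users who make a given error and m the number of naive users among the 15. If experienced users never make the error, P(seen at least once) = 1 − (1 − p)^m. Both p and m are assumptions; the documents give neither.

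| p | m = 15 | m = 12 | m = 10 | m = 7 |
|---|---|---|---|---|
| 5% | 53.7% | 46.0% | 40.1% | 30.2% |
| 10% | 79.4% | 71.8% | 65.1% | 52.2% |
| 15% | 91.3% | 85.8% | 80.3% | 67.9% |
| 20% | 96.5% | 93.1% | 89.3% | 79.0% |

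For p = 10%: 1 − 0.9^15 = 1 − 0.206 = 0.794, and 1 − 0.9^10 = 1 − 0.349 = 0.651.

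The loss is smaller if experience only partly protects. If the 5 experienced users make the error at half the naive rate (5%), the probability is 1 − 0.9^10 × 0.95^5 = 1 − 0.349 × 0.774 = 0.730.

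**2. Chance that a setting is missing.** If recruits were a random draw and a setting supplied a share s of them, P(none of 15) = (1 − s)^15. For s = 10% this is 0.9^15 = 20.6%; for s = 5% it is 0.95^15 = 46.3%. With four equally common settings, the chance that at least one is absent is 4 × 0.75^15 − 6 × 0.5^15 + 4 × 0.25^15 = 5.3%. Recruitment is local and not random, so these figures are only a guide. The protocol would permit all 15 from one setting.

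**3. What a floor of 4 per setting gives.** Three named settings × 4 = 12 places, leaving 3 free. An error made by 30% of users in a setting is seen at least once among 4 with probability 1 − 0.7^4 = 76.0%.

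**4. Recruitment burden of the exclusion.** If a fraction d of candidates has prior LunulaLaser use or training (assumed), finding 15 without it means screening 15/(1 − d): about 19 at d = 20%, 23 at d = one third and 30 at d = 50%. The enrolled number stays at 15.

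**The case against.** The best defense is that this was a stated decision. Section 6.1.1 goes through the user characteristics and concludes that none needs specific evaluation, and the intended population is simply employees of these facilities. The predicate was cleared for prescription use while these users work in non-clinical facilities, so few may have met it. Nothing in the documents suggests that 5 or 8 of 15 would have. The user eligibility form (Appendix D) is not among the pages available and may ask about experience.

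Part of this stands: the share of experienced recruits is unknown, so masking is a possibility and not a demonstrated bias. But the decision in 6.1.1 rests on a typical user profile without data, in the same section that rates knowledge of similar devices as helpful. Whatever Appendix D records, the criteria in 6.1.1.1 give no ground for excluding anyone on it.

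Four stronger readings are tempting and are not supported:

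- *The pass rate is inflated by some number of points.* Section 11.1 classifies each user as pass or fail and sets no study-level rate or threshold. Error detection is the relevant measure.
- *Anyone with Zerona experience should be excluded.* Section 6.1.1 treats similar-device knowledge as an acceptable trait, and the earlier study's users were of a comparable kind. The documents do not say that they were the same people or sites. Removing them could remove genuine intended users.
- *The missing literacy check makes failures impossible to interpret.* Weak readers would tend to fail more often, which works against the sponsor. Debriefing, knowledge tasks and root-cause analysis exist to explain failures, and applicable licensure and consent review are partial screens. Conversely, a sample of strong readers could leave the stated reading level untested.
- *The settings are shown to differ.* The documents give no evidence that task performance varies by facility. The point is only that the plan could not detect it if it did.

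**Conclusion.** The concern holds in two parts. First, the criteria do not secure the untrained user on which the design in 4.1 and 7.2.3 depends, because prior use of or training on the identical prescription device is no bar to entry. Second, they allow a sample from a single facility type to support a claim about all of them.

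The size of the first part cannot be fixed from the documents. In the illustration, the chance of seeing an error with a 10% naive rate falls from 79% to 65% when 5 of 15 users are experienced and immune to it, and to 73% if they make it half as often. With no experienced recruits there is no loss. For the second part, under random recruitment a setting with a 10% share would be absent about one time in five. These are design weaknesses worth correcting before enrollment. They do not show that the sample size is wrong or that the result would be biased.

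**What to change.** In 6.1.1.1, add one exclusion: prior use of, or training on, any LunulaLaser. On the screening form, record but do not exclude experience with Zerona or similar devices and participation in the sponsor's earlier usability study. In Section 11, report pass/fail and use errors with and without those users.

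In 6.1.1.3, within the same 15, require at least 4 users from each of the three named settings in 6.2, and list errors by setting. The floor does not cover comparable facilities; the 3 remaining places may be used for them. A short check of the reading level stated in 6.1.1 is optional.

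The cost is a few screening questions and slower recruitment. The sample size does not change. The pass count may come out less favorable than it would with experienced users included.
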